### **8.1.2 ORR and DOR**

For ORR and DOR as assessed by BICR, ORR will be computed in each of the 3 treatment groups along with the exact 95% CI using Clopper-Pearson method. An estimate of the difference in ORRs and corresponding 95% CI between each pair of treatment arms will be calculated using CMH methodology and adjusted by the stratification factors as specified in [Section 7.1.1](#). The stratified odds ratios (Mantel-Haenszel estimator) between each pair of treatment arms will be provided along with the 95% CI. DOR for each of 3 treatment groups will be estimated and overlaid using KM product limit method for subjects who achieve PR or CR. Median values along with two-sided 95% CI will be calculated.

These analyses will be produced for

- All concurrently randomized subjects to the 3 arms with measurable disease (BICR)
- All concurrently randomized subjects to the 3 arms with measurable disease (BICR) and PD-L1 CPS  $\geq 5$
- All concurrently randomized subjects to the 3 arms with measurable disease (BICR) and with PD-L1 CPS < 5.
- All randomized subjects to the 3 arms with measurable disease (BICR)
- All randomized subjects to the 3 arms with measurable disease (BICR) and PD-L1 CPS  $\geq 5$
- All randomized subjects to the 3 arms with measurable disease (BICR) and PD-L1 CPS < 5.

## **9 CONVENTIONS**

The following conventions may be used for imputing partial dates for analyses requiring dates:

- For missing and partial adverse event onset dates, imputation will be performed using the Adverse Event Domain Requirements Specification.

- Missing and partial Non-Study Medication Domain dates will be imputed using the derivation algorithm described in [Section 4.3.3](#) of BMS Non-Study Medication Domain Requirements Specification.

For death dates, the following conventions will be used for imputing partial dates:

- If only the day of the month is missing, the 1st of the month will be used to replace the missing day. The imputed date will be compared to the last known date alive and the maximum will be considered as the death date.
- If the month or the year is missing, the death date will be imputed as the last known date alive.
- If the date is completely missing but the reason for death is present the death date will be imputed as the last known date alive

For date of progression, the following conventions will be used for imputing partial dates:

- If only the day of the month is missing, the 1st of the month will be used to replace the missing day.
- If the day and month are missing or a date is completely missing, it will be considered as missing.
- In case of the date of death is present and complete, the imputed progression date will be compared to the date of death. The minimum of the imputed progression date and date of death will be considered as the date of progression.

For other partial/missing dates, the following conventions may be used:

- If only the day of the month is missing, the 15th of the month will be used to replace the missing day.
- If both the day and the month are missing, “July 1” will be used to replace the missing information.
- If a date is completely missing, it will be considered as missing.

The following conversion factors will be used to convert days to months or years:

$$1 \text{ month} = 30.4375 \text{ days and } 1 \text{ year} = 365.25 \text{ days.}$$

Duration (eg, DoR, etc) will be calculated as follows:

$$\text{Duration} = (\text{Last date} - \text{first date} + 1)$$

All statistical analyses will be carried out using SAS (Statistical Analysis System software, SAS Institute, North Carolina, USA) unless otherwise noted.

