3.1.3 Follow-up Phase

- Begins when the decision is made to discontinue a subject from study therapy.
- After completion of the first 2 follow-up (FU) visits (30 days [± 7 days] from last dose and 84 days [± 7 days] from FU1), subjects will be followed by clinic visit or phone contact every 3 months (± 14 days) or more frequently as needed for survival status and subsequent anti-cancer therapy.
- Subjects who discontinue treatment for reasons other than PD will continue to have tumor assessments (until PD) every 6 weeks (± 7 days) up to and including Week 48, then every 12 weeks (± 7 days) thereafter.
- Subjects will be followed for drug-related toxicities until these toxicities resolve, return to baseline or are deemed irreversible. All toxicities will be documented for a minimum of 100 days after the last dose of study drug.
- Patient-reported questionnaires EQ-5D-3L, GaCS from the FACT-Ga, and the FACT-G7 will be collected every 3 months (± 14 days) via phone contact or in-person visit.
- The biomarker sampling will continue as per protocol defined schedule

Study follow-up assessment data are to be collected as outlined in Table 5.1-5.

The start of the trial is defined as the first visit for the first subject screened. End of trial is defined as the last visit or scheduled procedure shown in the Time & Events schedule for the last subject. Study completion is defined as the final date on which data for the primary endpoint was or is expected to be collected, if this is not the same.

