3.6.2 Lost to Follow-Up

All reasonable efforts must be made to locate subjects to determine and report their ongoing status. This includes follow-up with persons authorized by the subject as noted above. Lost to follow-up is defined by the inability to reach the subject after a minimum of three documented phone calls, faxes, or emails as well as lack of response by subject to one registered mail letter. All attempts should be documented in the subject's medical records. If it is determined that the subject has died, the site will use permissible local methods to obtain the date and cause of death.

If investigator's use of third-party representative to assist in the follow-up portion of the study has been included in the subject's informed consent, then the investigator may use a Sponsor-retained third-party representative to assist site staff with obtaining subject's contact information or other public vital status data necessary to complete the follow-up portion of the study. The site staff and representative will consult publicly available sources, such as public health registries and databases, in order to obtain updated contact information. If after all attempts, the subject remains lost to follow-up, then the last known alive date as determined by the investigator should be reported and documented in the subject's medical records.

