### 4.1.1 Overall Survival

Overall Survival is defined as the time from the date of randomization to the date of death from any cause. For subjects that are alive, their survival time will be censored at the date of last contact date (or “last known alive date”). Overall survival will be censored at the date of randomization for subjects who were randomized but had no follow-up.

Primary objective of the study is the comparison of OS between nivo+chemo and chemo in PD-L1 CPS  $\geq$  5 subjects.

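### When the month of death is missing, the SAP drops a recorded year, so an imputed OS date can contradict the record (low severity)

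*SAP*

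**What the plan says.** SAP Section 4.1.1 makes the death date the event time: "Overall Survival is defined as the time from the date of randomization to the date of death from any cause". Section 9 introduces its death-date rules in firm terms: "For death dates, the following conventions will be used for imputing partial dates". There are three rules.

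- **Only the day missing.** The first of the recorded month is used, with a floor: "The imputed date will be compared to the last known date alive and the maximum will be considered as the death date". The known month and year survive.
- **Month or year missing.** "If the month or the year is missing, the death date will be imputed as the last known date alive". There is no comparison with a recorded year.
- **Whole date missing.** "If the date is completely missing but the reason for death is present the death date will be imputed as the last known date alive".

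Other rules in the same SAP keep a known year. The Section 9 rule for remaining dates opens "If both the day and the month are missing" and then uses 1 July of that year. Appendix 2 completes procedure dates, and surgery dates not collected on the prior-surgery page, as the later of 1 January of the known year and the first dose date.

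**The concern.** A death with a known year and an unknown month gets the same date as a death with no date at all. If last contact was before 1 January of the recorded year, the imputed date falls in a calendar year that the record shows the subject survived. The SAP gives no reason for treating death, which defines a primary endpoint, less informatively than a surgery date.

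Such records are possible. Protocol Section 3.6.1 allows public information to establish vital status after withdrawal of consent. Section 3.6.2 adds third-party tracing and registries for lost subjects, and says: "If it is determined that the subject has died, the site will use permissible local methods to obtain the date and cause of death". These subjects may have had no contact for longer than the planned interval.

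None of the OS supportive analyses in SAP Sections 7.5.2.5 and 7.5.3.2 varies the death-date imputation, and no count of imputed death dates by arm is planned. The accuracy of some OS event times is at stake, with possible knock-on effects on Kaplan-Meier estimates, hazard ratios and the restricted mean survival times in Section 8.1.1.

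**Working it through.** The plan states no figure for this rule, so there is none to reproduce. The check applies the rule to examples, asks how often it would misplace a death, and sizes the effect on the hazard ratio.

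**1. The rule on example dates.** Assumed randomization is 15-Jan-2018. OS in months = (death date − randomization date + 1) / 30.4375, using the duration and conversion conventions of SAP Section 9. The alternative is the later of 1 January of the recorded year and the last known alive date.

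| Last known alive | Recorded death | SAP rule | Year-keeping rule |
|---|---|---|---|
| 20-Nov-2018 | 2019 | 310 / 30.4375 = 10.18 | 352 / 30.4375 = 11.56 |
| 01-Jun-2018 | 2020 | 138 / 30.4375 = 4.53 | 717 / 30.4375 = 23.56 |
| 10-Feb-2019 | 2019 | 392 / 30.4375 = 12.88 | 12.88 (same) |

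The first two SAP dates contradict the record. The third does not, because last contact already lies in the recorded year.

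**2. How much of the error the alternative removes.** With last contact on 15-Nov-2018 and death recorded as 2019, the true date is 47 days (1-Jan-2019) to 411 days (31-Dec-2019) after the SAP date. The alternative removes the 47 days that contradict the record. It leaves 0 to 411 − 47 = 364 days that no rule can recover.

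**3. How often a month-missing death is misplaced by year.** Assume deaths uniform over the calendar year and the gap from last contact to death uniform from 0 to g months, with g at most 12. The share with last contact in an earlier year is the mean gap over 12, that is (g/2)/12 = g/24.

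- g = 3 (the planned interval): 3/24 = 12.5%
- g = 3.5 (about 14 days later): 14.6%
- g = 6: 25%
- g = 12: 50%

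**4. Effect on the hazard ratio, by share of deaths.** Simulation inputs are the OS hazards in SAP Table 5.2.1-3 (hazard ratio 1 for 6 months, then 0.65), 554 subjects, 25.4 months of accrual (assumed uniform) and analysis at 49.4 months. This gives a control median of 11.1 months (plan 11.1), 470 final events (plan 466) and 407 interim events (plan 395, so 3% high; the accrual pattern is not stated). The share of deaths with a missing month is assumed.

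| Month-missing deaths | Gap (months) | True dates | SAP rule | Year-keeping |
|---|---|---|---|---|
| 2%, both arms | 0–3 | 0.737 | 0.737 | 0.737 |
| 5%, both arms | 0–12 | 0.738 | 0.738 | 0.738 |
| 5%, control only | 0–12 | 0.737 | 0.727 | 0.730 |
| 10%, control only | 0–12 | 0.736 | 0.715 | 0.721 |

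**5. Effect by number of deaths, at the size in SAP Appendix 5** (949 subjects). Ten affected control deaths and two affected nivolumab plus chemotherapy deaths are assumed.

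| Gap (months) | True dates | SAP rule | Year-keeping |
|---|---|---|---|
| 6 | 0.741 | 0.736 | 0.737 |
| 12 | 0.737 | 0.727 | 0.732 |
| 0–3.5 | 0.7389 | 0.7376 | 0.7377 |

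Reversing the 10:2 split at a 6-month gap raises the hazard ratio by about 0.006. Five deaths in each arm change it by about 0.001 at most. For scale, with the 800 final events expected in Appendix 5, the standard error of the log hazard ratio is about 2/√800 = 0.071, or roughly 0.05 on the hazard-ratio scale.

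**The case against.** The strongest case against is about size and timing, and most of it stands.

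- **Narrow trigger.** Three conditions must coincide. Protocol Section 3.1.3 says that "subjects will be followed by clinic visit or phone contact every 3 months", and Section 3.6 allows extra survival requests outside that window. Nothing says that tracing returns a year only.
- **Dating deaths early is not peculiar to this rule.** The day-missing rule and the proposed fix also take the earliest date consistent with the record. The defect is that this rule goes earlier than the record allows.
- **Some visibility exists.** SAP Sections 7.5.2.4, 7.5.3.1 and 7.6.1 require by-subject OS and death listings, although they do not ask for imputed dates to be marked.
- **The nivolumab plus chemotherapy OS is already reported.** The SAP document history places version 5.0 after that interim analysis and its study report. Appendix 5 passes on alpha of 0.035, which under Section 7.5.1 means both primary endpoints were positive. Replacing the derivation now would alter a primary endpoint after its formal test.

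A reader might infer that, because the trial is open label, deaths traced after withdrawal cluster in the chemotherapy arm and the rule therefore favours the experimental arm. The documents give no counts by arm and no reason to expect that split, and the reverse split moves the result the other way.

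None of this answers the basic point: for some records the rule yields a date that the record excludes, and the SAP handles the same situation better elsewhere.

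**Conclusion.** The point holds at low severity. By its plain wording, SAP Section 9 discards a recorded year of death when the month is missing. It produces an OS date that contradicts the record whenever last contact fell in an earlier calendar year.

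The number of affected deaths is unknown and probably small. Balanced between arms, they leave the hazard ratio essentially unchanged. In the assumed one-sided scenarios the SAP rule shifts it by 0.001 to 0.021, and the year-keeping rule recovers 0.0001 to 0.006. Those shares, gaps and splits are assumptions, so no direction of bias can be claimed. A reader might also take this as grounds to doubt the reported nivolumab plus chemotherapy OS result; the documents do not support that. The case for change is correctness and consistency at very little cost.

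**What to change.** In SAP Section 9, split the second death-date rule. If the year is known and the month is missing, impute the later of 1 January of that year and the last known alive date. Keep the last known alive date alone only when the year is also missing.

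- **Nivolumab plus ipilimumab vs chemotherapy OS** (24-month time point): adopt the revised rule if the analysis has not yet been performed.
- **Nivolumab plus chemotherapy vs chemotherapy OS:** leave the reported analysis as it is and run the revised rule as a labelled sensitivity analysis.
- **Both comparisons:** report the number of imputed death dates by arm and by type (day missing, month missing, wholly missing).

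The cost is one sentence in the SAP, one line of derivation code, a small table and one sensitivity run. If the table shows no month-missing deaths with an earlier-year last contact, the matter is closed.

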## 10 CONTENT OF REPORTS

At the time of first analysis time point (12 months minimum follow-up), the final analysis of PFS and interim analysis of OS in PD-L1 CPS $\geq$ 5 randomized subjects in the nivo+chemo vs chemo arms will be performed. Below are potential scenarios for the planning of contents report:

- 1) If both of the primary endpoints are not meeting the pre-specified statistical significance criteria, the study will continue and there is no unblinding of either endpoint. As such, no report is planned.
- 2) If PFS meets the pre-specified statistical criteria, a clinical study report for nivo+chemo vs. chemo will be written with all the analyses listed in this SAP except for these analyses related to OS.
- 3) If both primary endpoints meet the pre-specified statistical significance or only OS meets the statistical significance, a clinical study report for nivo+chemo vs. chemo will be written with all analyses listed in this SAP.
- 4) There will be no analysis performed for the nivo+ipi vs. chemo comparison.

At the second analysis time point (24 months minimum follow-up), a report for nivo+ipi vs. chemo will be written with all analyses listed in this SAP. A report for nivo+chemo vs chemo will be written with the primary endpoint(s) that have not yet reported at the first time point if any.

Refer also to the Data Presentation Plan for mock-ups of all tables and listings.

## 11 DOCUMENT HISTORY

**Table 11-1: Document History**

Version Number	Author(s)	Description
1 25-Apr-2017	██████████	Original SAP based on revised Protocol 02
2 02-Dec-2019	██████████	Updated to align with IO CORE SAP Updated to reflect revised protocol 09.

**Table 11-1: Document History**

Version Number	Author(s)	Description
3 29-May-2020	[REDACTED]	
Based on revised protocol 09.
 
Minor updates from SAP version 2.0 to add/modify sensitivity analyses and other minor edits. Details are summarized below:
 
 
• Section 7.5.2.2, 7.5.2.5 and 7.5.3.2 Replace the Fleming-Harrington test F(0,1) by the max combo in case of NPH.
 
• added potential sensitivity analysis in case of imbalance in PD-L1 CPS<math>\geq</math>5 group in Sections 7.5.2.2, 7.5.2.5 and 7.5.3.2
 
• Update blinding and unblinding Section 2.3 regarding unblinding of the PFS results but not OS results in case that PFS is positive but OS is negative at the interim.
 
• Section 4.1.2, added some text to state that PFS regardless of subsequent therapy is considered as primary analysis by EMA. The PFS account for subsequent therapy is the primary endpoint of the study and will be the basis of the primary test.
 
• For swimmer plot for ADA and Nab in relation to efficacy endpoint, added BOR per BICR
 
• Section 7.8.3.2, corrected typo, 6 KM curves for each combination of biomarker status and treatment
 
• Corrected 24-Mar to 27-Mar in definition of All randomized subjects for nivo+chemo vs chemo. It has no impact on datasets, change was made for consistency.
 
• Added AE tables for the all treated subjects with CPS<math>\geq</math>5. Added IMAE outputs for all treated subjects with CPS<math>\geq</math>5.
 
• Added surgery to the list of concurrent prohibited anti-cancer therapy to reflect protocol.
 
• Changed “Planned Chemotherapy” to “Chemotherapy” for subgroup analyses as we will use the Chemotherapy as treated.
 
• Correction to Time Window for EQ-5D-3L, FACT-Ga, for the survival for follow-up.
 
• Removed Siewert-Stein classification from the list of subsets for PFS, OS and ORR as this is collected only for GEJ.
 
• Added Baseline albumin (< LLN, <math>\geq</math>LLN) to the list of subsets for PFS, OS and ORR
 
• Censoring efficacy endpoints for subsequent therapy. Subjects are censored for radiotherapy with reason curative and added reason palliative.
 
• Added UNKNOWN category for MSI
 
• added appendix 4 with analyses of data from China
 

**Table 11-1: Document History**

Version Number	Author(s)	Description
4.0 04-Aug-2020	[REDACTED]	Added Appendix 5 to update the expected number of subjects, expected number of PFS and OS events and updated power based on the actual CPS $\geq$ 5 prevalence. The prevalence was estimated using the locked database of July 10, 2020. The estimation was done in a blinded manner using the pooled estimate for the 3 arms.
5.0 14-May-2021	[REDACTED]	
This update was implemented after the analysis of PFS and OS IA for nivo+chemo vs chemo for which the CSR was written. The updates do not affect any of the planned analyses for nivo+ipi vs chemo. The updates include:
 
 
• Update to Section 7.4.1, to allow reporting of the overall RDI for nivolumab in the nivo+ipi treatment arm, the formula was changed.
 
• Specific section (Section 7.10) related to COVID 19 data reporting.
 
• Specific section (Section 8) with exploratory analyses to support the justification of the ipilimumab contribution in the nivo+ipi regimen.
 

## **APPENDIX 1 TIME-TO ONSET AND TIME-TO RESOLUTION DEFINITION AND CONVENTIONS FOR SELECT ADVERSE EVENTS, IMMUNE-MEDIATED ADVERSE EVENTS AND EVENTS OF SPECIAL INTEREST**

### **Time-to onset definition**

Time-to onset of AE (any grade) for a specific category is defined as the time between the day of the first dose of study treatment and the onset date of the earliest AE (of any grade) in this category.

The time-to onset of AE (grade 3-5) for a specific category is defined similarly with an onset date corresponding to a grade 3-5 AE.

Time-to onset of drug-related AE (any grade or grade 3-5) for a specific category is defined similarly but restricted to drug-related AE.

Time-to onset for a specific subcategory is defined similarly but restricted to event of this subcategory.

### **Time-to resolution definition**

In order to derive the time-to resolution, overlapping or contiguous AEs within a specific category or subcategory will be collapsed into what will be termed “clustered” AEs. For example, if a subject (without pre-treatment AE) experienced an AE from 1st to 5th January, another AE (with different PT but within same category) from 6th to 11th January and same AE from 10th to 12th January, these will be collapsed into one clustered AE from 1st to 12th January. [Table 1](#) is summarizing key derivation steps for each type of clustered AEs.

Time-to resolution of AE (any grade) for a specific category is defined as the longest time from onset to complete resolution or improvement to the grade at baseline among all clustered AEs experienced by the subject in this category per adverse event criteria category. Events which worsened into grade 5 events (death) or have a resolution date equal to the date of death are considered unresolved. If a clustered AE is considered as unresolved, the resolution date will be censored to the last known alive date. Improvement to the grade at baseline implies that all different events in the clustered adverse event should at least have improved to the corresponding (ie, with same preferred term) baseline grade. This measure is defined only for subjects who experienced at least one AE in the specific category.

The time-to resolution of AE (grade 3-5) for a specific category is defined similarly with an onset date corresponding to a grade 3-5 AE.

Time-to resolution of drug-related AE (any grade or grade 3-5) for a specific category is defined similarly but restricted to drug-related AE.

The time-to resolution of AE (any grade or grade 3-5, drug-related or all) where immune modulating medication was initiated is defined similarly. For data presentation not restricted to IMAE, the additional condition that the subject started an immune modulating medication during the longest AE resolution period will be applied.

Time-to resolution for a specific subcategory is defined similarly but restricted to event of this subcategory.

**Table 1 Derivation of Clustered AE**

Type of clustered AE	Derivation
Any grade	Collapse any on-treatment AE from the same category
Drug-related of any grade	Collapse any on-treatment drug-related AE from the same category
Grade 3-5	Collapse any on-treatment AE from the same category. Resolution will be based on the onset date of the earliest grade 3-5 records (if no grade 3-5 record, clustered AE is excluded)
Drug-related of Grade 3-5	Collapse any on-treatment drug-related AE from the same category Resolution will be based on the onset date of the earliest grade 3-5 record (if no Grade 3-5 record, clustered AE is excluded)

The algorithm for collapsing adverse event records is using the following conventions:

For each subject and specified category, the corresponding adverse event records will be collapsed when:

- 1) Multiple adverse event records have the same onset date.
- 2) The onset date of an event record is either the same day or 1 day later than the resolution date of a preceding event record (contiguous events).
- 3) The onset date of an event record is after the onset date and prior to or on the resolution date of a preceding event record (overlapping events).

